Post-Market Evaluation of the Rotation Medical Rotator Cuff System

Protocol Number 2014.05.12

REVISION C

January 2018

Rotation Medical, Inc.

[name]

This study will be conducted in accordance with the protocol and applicable regulatory requirements.

CONFIDENTIAL INFORMATION

No use or disclosure of information contained within this document is permitted without prior written authorization from Rotation Medical, Inc.

STUDY CONTACT INFORMATION

Study Sponsor:

Rotation Medical, Inc. [name]

Study Contact:

[name] Rotation Medical, Inc. [name] [contact] [contact] E-mail: [contact] ROTATION MEDICAL, INC. PROTOCOL SIGNATURE PAGE

Post-Market Evaluation of the Rotation Medical Rotator Cuff System

PROTOCOL NO. 2014.05.12

Revision C

January 2018

I have read this study protocol and the signature below constitutes approval of this protocol and any attachments, and provides the necessary assurances that this study will be conducted in accordance to all stipulations of the protocol and in compliance with applicable local legal and regulatory requirements and applicable U.S. federal regulations including 21 CFR Part 50 (Protection of Human Subjects) and 21 CFR Part 56 (Institutional Review Boards).

Clinical Site Name

Site Principal Investigator Signature

Date

Site Principal Investigator Printed Name

PROTOCOL STUDY SYNOPSIS				
Title:	Post-Market Evaluation of the Rotation Medical Rotator Cuff System			
Study Devices:	Rotation Medical Rotator Cuff System [™] (Cleared for commercial use by the U.S. Food and Drug Administration: K140300; K131637; K131635; K122048)			
Study Design:	Prospective, non-randomized, post-market study			
Enrollment:	Up to 150 subjects will be treated			
Inclusion	1. At least 21 years of age			
Criteria:	 Art feate 21 years of age Rotator cuff tear requiring surgery that meets either criterion A or B: A. Medium or large partial-thickness tear or very small full-thickness tear of the supraspinatus tendon planned for standalone treatment (no surgical repair with sutures/suture anchors) with the bioinductive implant B. Medium or large full-thickness tear primarily of the supraspinatus tendon planned for treatment with the bioinductive implant B. Medium or large full-thickness tear primarily of the supraspinatus tendon planned for treatment with the bioinductive implant adjunctive to surgical repair Chronic shoulder pain lasting longer than 3 months unresponsive to conservative therapy including, but not limited to, pain medication, physical therapy and injections MRI of the shoulder within 60 days prior to the study procedure Willing to comply with the prescribed post-operative rehabilitation program Willing to be available for each protocol-required follow-up examination Able to understand the informed consent process, including regulatory requirements such as HIPAA authorization, and document informed consent prior to completion of any study-related procedures Ability to read, understand, and complete subject-reported outcomes in English 			
Exclusion Criteria:	 Massive rotator cuff tears (≥ 5 cm) Acute rotator cuff tears less than 12 months from injury Previous rotator cuff surgery on the index shoulder Instability of the index shoulder Chondromalacia of index shoulder ≥ Grade 3 Fatty infiltration of the index shoulder rotator cuff muscle ≥ Grade 2 Calcification of the index shoulder rotator cuff Genetic collagen disease History of auto-immune or immunodeficiency disorders History of chronic inflammatory disorders Oral steroid use in last 2 months or injectable steroid use in last 4 weeks History of heavy smoking (> 1 pack per day) within last 6 months Hypersensitivity to bovine-derived materials Females of child-bearing potential who are pregnant or plan to become pregnant during the course of the study Currently involved in any injury litigation or worker's compensation claims relating to the index shoulder 			

	17. Enrolled, or plans to enroll, in another clinical trial during this study that		
	would affect the outcomes of this study		
	18. History of non-compliance with medical treatment, physical		
	therapy/rehabilitation, or clinical study participation		
	19. History of cognitive or mental health status that interferes with study		
	participation		
Study	To evaluate bioinduction of new tissue and tendon healing after implantation of		
Objective:	the Rotation Medical Bioinductive Implant used as either a standalone device or		
	adjunct to surgical repair in the treatment of supraspinatus tendon tears.		
Primary	Primary MRI assessment of the following:		
Outcomes:	1. Increase in tendon thickness		
	2. Integration of induced tissue with the underlying tendon and maturation of		
	the induced tissue		
	3. Amount of defect fill-in and characteristics of both the filled-in tissue within		
	the tendon tear and underlying tendon (nonsurgically-repaired tears only)		
	4. Rotator cuff re-tear rate		
Secondary	1. Safety		
Outcomes:	2. Procedure parameters		
	3. Change in American Shoulder and Elbow Society (ASES) scale		
	4. Change in Constant-Murley Shoulder score		
	5. Recovery		
	6. Subject satisfaction		
Study	Baseline		
Assessments	Procedure		
	Post-procedure follow-up: 3 months, 1 year, 2 years		
Sponsor:	Rotation Medical, Inc.		
	[name]		
Data	Rotation Medical Inc		
Management	[name]		
and	[name]		
Monitoring:	1 IYIIIOuul IVIIN 33447		

TABLE OF CONTENTS

1	INT	INTRODUCTION & RATIONALE8			
2	DE	VICE DESCRIPTION	.9		
	2.1	DEVICE DESCRIPTION	.9		
	2.2	PRINCIPLES OF OPERATION	10		
3	STU	JDY OBJECTIVE1	10		
4	STU	JDY DESIGN	1		
	4.1	SAMPLE SIZE	1		
	4.2	STUDY DURATION	11		
	4.3	PRIMARY OUTCOME MEASURES	11		
	4.3. 4.3.	2 Integration and Maturation of New Tissue	11		
	4.3.	3 Fill-In of Partial-Thickness Tears and Underlying Tendon Quality	11		
	4.3.	4 Re-tear Rate	11		
	4.4 4 4	SECONDARY OUTCOME MEASURES	12		
	4.4.	2 Procedure Parameters	12		
	4.4.	3 Change in American Shoulder and Elbow Society (ASES) Scale	12		
	4.4.	4 Change in Constant-Murley (Constant) Shoulder score	12		
	4.4. 44	5 Recovery	13		
5	ят.	ATISTICAL ANALVSIS DI AN	13		
3	517		15		
	5.1 5.2	HYPOTHESIS I ESTING, SAMPLE SIZE AND POWER	13		
6	5.2 FU		1.4		
0	ELI		14		
	6.1	INCLUSION CRITERIA	14		
_	0.2				
7	STU	JDY ASSESSEMENTS			
	ABLE		15		
1		7-1: SCHEDULE OF STUDY ASSESSMENTS1	15		
1.	7.1	7-1: SCHEDULE OF STUDY ASSESSMENTS	15 16 16		
1	7.1 7.2	7-1: SCHEDULE OF STUDY ASSESSMENTS	15 16 16		
1.	7.1 7.2 7.3 7.4	7-1: SCHEDULE OF STUDY ASSESSMENTS	15 16 16 16 16 17		

1 INTRODUCTION & RATIONALE

Musculoskeletal disorders are one of the most common causes of disability in the United States with approximately 50% of the adult population having experienced a chronic musculoskeletal condition lasting longer than 3 months.¹ After knee-related disorders, shoulders are the second most common joint causing chronic pain with an estimated 18.9 million adults affected. The direct cost of treating shoulder pain is approximately \$7 billion annually and this figure excludes the indirect cost burden (i.e., missed work, lost productivity).¹ With age, the prevalence of rotator cuff disease increases with an estimated 50% of individuals over 66 years of age having bilateral rotator cuff tears.^{2,3} Recent demographic and morphological studies of rotator cuff tears also show that these defects increase in size with time and painful tears tend to be larger than asymptomatic tears.^{2,4}

Persistent shoulder pain concomitant with a rotator cuff tendon tear is currently treated with arthroscopic subacromial decompression (ASD) with or without cuff repair depending on the size and morphology of the cuff tear. Decompression alone leaves the tendon tear structurally unmodified and does not prevent rotator cuff tear progression.^{5,6,7} Cuff repair as a treatment for rotator cuff tears often requires the resection of tendon from the bone and re-attachment using suture anchors.^{8,9,10} Estimates of re-tear rates following the completion and repair of small tears have been reported between 10% and 36%.^{8,9,11} Peri-operative morbidity and post-operative rehabilitation associated with rotator cuff tendon repair is more extensive for the patient than ASD alone.⁷

The Rotation Medical Bioinductive Implant is a bioabsorbable device that provides a layer of collagen over injured tendons. This device is indicated for the management and protection of tendon injuries in which there has been no substantial loss of tendon tissue and can be implanted either during mini-open or arthroscopic procedures. The device was first evaluated in a preclinical study of 23 sheep that was approved by the Colorado State University Institutional Animal Care and Use Committee. The device did not elicit an inflammatory response or a foreign body reaction and histological analyses confirmed the device was completely absorbed after six months with integration of the new tendinous tissue to the underlying host tendon and a fibrocartilagenous transition zone at the tendon-to-bone insertion site. Tendon thickness at the implant site increased by approximately 2.5 millimeters due to induction of new tendinous tissue and remained stable one year after surgery.¹²

The Rotation Medical Bioinductive Implant was further evaluated in a clinical study of 24 subjects who underwent implantation of the device and completed a minimum of one year follow-up. This study was approved by the Northern Sydney Central Coast Ethics Committee and registered in the Australian New Zealand Clinical Trials Registry [#ACTRN12611001082998]. The procedure was performed arthroscopically in 14 subjects while the other 10 subjects underwent a mini-open procedure. The median implant time was 15 minutes and all subjects were successfully implanted with no intent-to-treat failures. One patient experienced a return to pain 12 months after surgery that was associated with significant bursitis and an arthroscopic clean-up procedure was performed to debride the bursa. Despite the bursal reaction in this patient, tendon healing and tissue induction were not compromised.

Magnetic resonance imaging (MRI) at 3, 6, and 12 months after surgery provided evidence that the device consistently induced the formation of new, tendinous tissue that appeared well-integrated with each patient's native tendon tissue and showed progressive maturation over time. MRI observations were consistent with the histological results from prior sheep studies.¹³ Shoulder function and pain was also assessed at 3, 6 and 12 months after treatment using the ASES (American Shoulder and Elbow Surgery) and Constant (Constant-Murley) standard shoulder surveys.^{14,15} All of the scores at 12 months were significantly improved from baseline (p < 0.05) and improvement was comparable to published literature.¹⁶

2 DEVICE DESCRIPTION

2.1 **DEVICE DESCRIPTION**

There are three implantable components in the Rotation Medical Rotator Cuff System[™] (Figure 2-1).

- 1. Bioinductive implant: The device is made from highly purified reconstituted collagen fibers derived from bovine tendon and manufactured for Rotation Medical, Inc. by Collagen Matrix, Inc. (Oakland, New Jersey, USA). It is contraindicated for use in patients with a history of hypersensitivity to bovine-derived materials and this is an exclusion criterion for study participation. The device is designed to completely absorb within six to 12 months.
- 2. Tendon staples: The tendon staples are made from poly(L-lactide-co-D,L-lactide) in a molar ratio of 70% L-lactide to 30% D,L-lactide. Polylactide materials have been used in a variety of medical devices, such as bone anchors, bone pins, screws, plates, and spinal fusion cages. The tendon staples are designed to completely absorb within approximately 12 months.
- 3. Bone staples: The bone staples are made from polyetheretherketone (PEEK), which is a common polymer used for bone anchors in orthopedic surgery. The bone staples are not bioabsorbable.

The Rotation Medical Rotator Cuff System has been cleared by the U.S. Food and Drug Administration (FDA) [K140300; K122048; K131635; K131637]. The purpose of this post-market study is to collect and analyze outcomes data under a common protocol.

Figure 2-1: Rotation Medical Implantable System Components

The tendon and bone staplers used to affix the bioinductive implant to tendon tissue and the head of the humerus respectively are shown in **Figure 2-2**. These are designed as single-use devices.

Figure 2-2: Rotation Medical Single-Use Disposable Staplers

Tendon stapler

Bone stapler

2.2 PRINCIPLES OF OPERATION

No investigational devices or procedures will be used in this post-market study and all devices will be used according to their indications for use. Operation, indication, and instructions for use are described in the Instructions for Use (IFUs).

3 STUDY OBJECTIVE

To evaluate bioinduction of new tissue and tendon healing after implantation of the Rotation Medical Bioinductive Implant used as either a standalone device or adjunct to surgical repair in the treatment of supraspinatus tendon tears.

4 STUDY DESIGN

This is a prospective, non-randomized, single-arm multi-center study conducted under a common protocol designed to evaluate long-term outcomes following arthroscopic or mini-open implantation of the Rotation Medical Bioinductive Implant to treat high-grade partial thickness or small/medium/large (i.e. non-massive) full-thickness rotator cuff tears primarily involving the supraspinatus tendon.

4.1 SAMPLE SIZE

Up to 150 subjects will be enrolled and treated with the Rotation Medical Rotator Cuff System at up to 15 study sites in the United States.

4.2 STUDY DURATION

Enrollment is anticipated to take up to 12 months and all subjects will be followed for two years after surgery. Therefore, the overall study duration is estimated to be 36 months.

4.3 PRIMARY OUTCOME MEASURES

4.3.1 Increase in Tendon Thickness

Supraspinatus tendon thickness will be measured pre-operatively (baseline) and the total thickness of the tendon and any newly induced tissue at the implant site will be measured at each follow-up visit using magnetic resonance imaging (MRI). The mean (\pm SD) change in post-operative supraspinatus tendon thickness will be calculated at each follow-up interval.

4.3.2 Integration and Maturation of New Tissue

Integration and maturation of the newly induced tissue will be assessed by MRI at each post-operative follow-up. This outcome will assess, at a minimum, the following characteristics of the newly induced tissue: (i) presence or absence of a clear boundary between the device and the underlying tendon; (ii) presence or absence of a clear boundary between the newly induced tissue and the overlying deltoid muscle; (iii) maturation of newly induced tissue to resemble characteristics of underlying tendon tissue (versus debris or artifact).

4.3.3 Fill-In of Partial-Thickness Tears and Underlying Tendon Quality

For tendon defects treated by standalone use of the device (i.e., implantation without surgical repair using sutures/suture anchors), post-operative follow-up MRIs will be used to estimate the amount of defect fill-in with newly induced tissue and the quality of the filled-in tissue. In the absence of fill-in with newly induced tissue, defect progression (i.e., change in size relative to previous MRIs) will be assessed.

4.3.4 Re-tear Rate

Re-tear following rotator cuff repair will be assessed at each follow-up visit using MRI. Any new observable defect (i.e. loss in supraspinatus tendon continuity) will be classified as a re-tear.

4.4 SECONDARY OUTCOME MEASURES

4.4.1 Safety

Safety will be evaluated by any of the following adverse events that occur over the duration of the study:

- 1. Any death
- 2. All serious adverse events (SAE) regardless of relation to the device or procedure
- 3. Any non-serious adverse event (AE) that is classified as either device or procedurerelated
- 4. Any unanticipated adverse device effect (UADE)

Adverse events will be summarized by relation to the study devices or study procedure. Overall occurrence rate by event type will also be calculated.

4.4.2 Procedure Parameters

The following procedural parameters will be recorded on all subjects:

1. Device implant time: Mean $(\pm SD)$ implant time defined as follows:

Arthroscopic procedure: Time from introduction of the guide wire instrument into the subacromial space to completion of last staple

Mini-open procedure: Time from introduction of the bioinductive implant into the subacromial space to completion of the last staple

- 2. Procedure technical success: The proportion of subjects where the device was successfully delivered and affixed to target tendon location.
- 3. Device implant position: An intra-operative photograph(s) or video recording showing the implant location of the device and all tendon and bone staples will be obtained.

4.4.3 Change in American Shoulder and Elbow Society (ASES) Scale

The mean (\pm SD) overall patient-reported ASES score (Range: 0 to 100) will be calculated at baseline and each subsequent follow-up. In addition, matched-pair analyses between baseline and successive follow-up visits will be performed to determine the mean (\pm SD) change in overall ASES score after surgery. Mean (\pm SD) overall shoulder pain from the ASES survey (Range: 0-10) will also be analyzed separately at baseline and each post-operative follow-up visit.

4.4.4 Change in Constant-Murley (Constant) Shoulder score

The mean (\pm SD) overall Constant score (Range: 0 to 100) will be calculated at baseline and each subsequent follow-up. In addition, matched-pair analyses between baseline and successive follow-up visits will be performed to determine the mean (\pm SD) change in overall Constant score after surgery. Mean (\pm SD) overall shoulder pain from the Constant survey (Range: 0-15) will also be analyzed separately at baseline and each postoperative follow-up visit.

4.4.5 Recovery

The following post-operative recovery parameters will be reported after discharge from the from study procedure:

- 1. Sling time: cumulative number of days (mean \pm SD) index shoulder is in a sling
- 2. Rehabilitation time: cumulative number of completed rehabilitation or physical therapy (PT) visits (mean \pm SD) to treat index shoulder
- 3. Return to work: cumulative number of days (mean ± SD) between discharge and return to work (employed subjects only)
- 4. Return to normal daily activities (i.e. full, unrestricted activity): cumulative number of days (mean \pm SD) between discharge and return to normal daily activity

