5 STATISTICAL ANALYSIS PLAN

5.1 Hypothesis Testing, Sample Size and Power

This is a single-arm, non-blinded study. The primary, quantitative endpoint is increase in thickness of the supraspinatus tendon at the device implant location.

The hypothesis being tested is that the overall thickness of the supraspinatus tendon increases by a minimum threshold identified as the objective performance criterion (OPC):

H_O: $d \le OPC$ H_A: d > OPC;

where "d" is the difference in supraspinatus tendon thickness at the location of the device at each follow-up interval (Follow-Up – Baseline).

Based upon finite element analysis (FEA) modelling, the theoretical reduction in tendon microstrains from the addition of 2 millimeters of new tendinous tissue at the tear site is 40% for articular-sided, partial thickness tears and 47% for bursal-sided tears. Data from clinical use of the device demonstrated a mean increase in tendon thickness of 2.39 ± 0.95 millimeters at one year.¹³

Sample size was estimated using PASS 2008¹⁷ and a one-sided one-sample t-test. The one-sided alpha level was set at 0.025. The value of d (mean of outcome measure) was set at 2 millimeters. Sample size calculations were made using powers of 80%, 85% and 90% and a one-sided alpha of 0.025 (non-inferiority; alpha-splitting) using a one-sample t-test.

Using a minimum OPC of 1.0 millimeter, a standard deviation of 1.0 millimeter, and 90% power, a total sample size of 13 subjects is adequate to test this hypothesis. Although adequate power is obtained with 13 subjects, to adjust for attrition and allow up to 30 evaluable subjects at 24-month follow-up meeting inclusion criterion 2A and another 30 evaluable subjects meeting inclusion criterion 2B, up to 150 subjects will be enrolled.

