7.7 FOLLOW-UP ASSESSMENTS

All subjects will undergo post-operative study assessments at 3 months, 1 year, and 2 years after discharge from the study procedure as described below and summarized in **Table 7.1**.

7.7.1 3-Month (± 15 Days) Follow-Up

- 1. Perform an MRI per the Sponsor imaging guidelines.
 - Provide the Sponsor with a de-identified digital copy of, or access to, the MRI.
- 2. Administer the Constant-Murley shoulder survey.
 - Range of motion (ROM) should be measured with a goniometer and strength should be measured with a dynamometer. NOTE: Strength or ROM testing at 3-Month Follow-Up may not be possible due to subject discomfort or ongoing rehabilitation and therefore missed or incomplete strength or ROM testing at this visit will not be considered as a protocol deviation.
- 3. Administer the ASES shoulder survey.
 - Completion of the ASES patient assessment section is required. Completion of the ASES physician assessment section is optional since ROM and strength are assessed during administration of the Constant-Murley survey.
- 4. Administer the recovery/satisfaction questionnaire.
- 5. Record prescription medications.
 - *Record any prescription medications the subject is taking at the time of the follow-up visit to treat his/her index shoulder.*
- 6. Record any new adverse events and update the status of any ongoing, previouslyreported adverse events.
- 7. Report any new revision/additional shoulder surgeries performed on the index shoulder.

7.7.2 1-Year (± 45 Days) Follow-Up

- 1. Perform an MRI per the Sponsor imaging guidelines.
- Provide the Sponsor with a de-identified digital copy of, or access to, the MRI.
- 2. Administer the Constant-Murley shoulder survey.
 - *Range of motion (ROM) should be measured with a goniometer and strength should be measured with a dynamometer.*
- 3. Administer the ASES shoulder survey.
 - Completion of the ASES patient assessment section is required. Completion of the ASES physician assessment section is optional since ROM and strength are assessed during administration of the Constant-Murley survey.
- 4. Administer the recovery/satisfaction questionnaire.
- 5. Record prescription medications.

- *Record any prescription medications the subject is taking at the time of the follow-up visit to treat his/her index shoulder.*
- 6. Record any new adverse events and update the status of any ongoing, previouslyreported adverse events.

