8.2 SERIOUS ADVERSE EVENT (SAE)

A Serious Adverse Event (SAE) includes any of the following events:

- Results in death
- Is life threatening
- Requires subject hospitalization or prolongation of existing hospitalization
- Requires invasive surgical intervention to fix the problem
- Results in persistent or significant disability/incapacity
- Is considered an important medical event

An important medical event that may not meet one of the above definitions might be considered as an SAE if it jeopardizes the health of the subject or requires surgical intervention to prevent one of the outcomes listed in the above definition. Elective hospitalization after the procedure that was planned prior to subject enrollment is not to be considered as an SAE.

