12 RISKS AND BENEFITS

12.1 RISKS AND RISK MITIGATION

Study patients will be informed of all known potential side effects and complications associated with the study assessments and study procedure prior to enrollment in the study.

There are no known incremental risks to the subject for participating in the study. The risks associated with participating in this study are the same as if the patient is treated outside of the study using the same commercially-available device and include the following potential risks of rotator cuff surgery performed under general or regional anesthesia:

- Tissue inflammation
- The need for repeated surgery because tendons do not heal properly or tear again
- Pain or stiffness that won't go away
- Fever and/or infection
- Complication from anesthesia
- Nerve or blood vessel damage
- Adverse reaction to device

In addition, subjects will be required to undergo MR imaging. MRI is generally a welltolerated procedure and there is no ionizing radiation involved with MR imaging The potential risks are minimal and include claustrophobia, coil element heating and peripheral nerve stimulation, although the latter two are considered highly unlikely, given that the subjects will be imaged within preset safety guidelines to eliminate peripheral nerve stimulation. Coil element heating ranges from a mild sensation of heat to a potential burn. This is considered highly unlikely, as the coils have all undergone extensive testing and clinical use, and special pads are placed surrounding all contact points.

All Investigators will undergo training and subjects will be screened and evaluated for medical histories/conditions that may compromise safe, successful completion of any of the study assessments or performance of the device. Subjects with a known hypersensitivity to bovine-derived materials will not be enrolled in the study.

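### Return to work and return to full activity are summarised only as mean ± SD days, so the planned summary does not show how many subjects did not return

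*Combined protocol and SAP*

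**What the plan says.** Recovery is one of the six secondary outcomes in the synopsis. Section 4.4.5 lists four recovery parameters, and two of them are times to an event:

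- Return to work: "cumulative number of days (mean ± SD) between discharge and return to work (employed subjects only".
- Return to activity: "Return to normal daily activities (i.e. full, unrestricted activity): cumulative number of days", counted from discharge and again given as mean ± SD.

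The apparent source is the questionnaire in section 7.7 ("Administer the recovery/satisfaction questionnaire"), given at 3 months, 1 year and 2 years. Its items are not in the documents.

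Elsewhere the plan names a rate or proportion when it wants one. Section 4.4.1 states "Overall occurrence rate by event type will also be calculated", and section 4.4.2 defines technical success as "The proportion of subjects where the device was successfully delivered and affixed to target tendon location". Section 4.4.5 names neither. Section 5 covers the tendon-thickness test, sample size, and interim and subgroup analyses. It has no missing-data or censoring rule. Sections 7.10 and 7.11 govern withdrawal and exit but do not say what an exiting subject contributes to the recovery outcomes.

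**The concern.** Days from discharge to return exist only for someone who has returned. A subject still off work or still restricted at the last questionnaire, or lost before reporting a return, has no value. The documents give no assigned value, censoring rule or count for such subjects. Followed literally, the plan averages over returners and leaves the rest out of sight.

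Subjects without a reported return are foreseeable. Section 5.1 sets enrolment "to adjust for attrition and allow up to 30 evaluable subjects at 24-month follow-up meeting inclusion criterion 2A", so some attrition is expected. Section 12.1 lists lasting pain or stiffness and "The need for repeated surgery because tendons do not heal properly or tear again" among the risks. It gives no rates, and those risks are not the same thing as failure to return, but they make universal return an unsafe assumption. The activity endpoint also requires unrestricted function, which is a demanding standard. Section 5.2 allows interim summaries at any time, when more subjects will not yet have returned.

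At stake is whether a reader of the recovery results can tell a quick recovery in nearly everyone from a quick recovery in those who recovered.

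**Working it through.** **The plan's own figure.** The documents state no figure for the recovery outcomes. The only sample-size figure, 13 subjects, concerns tendon thickness. It reproduces (one-sided one-sample t-test, alpha 0.025, difference 1 SD: power 88.3% at 12 and 91.1% at 13) and this point does not affect it.

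**Inputs.** From the documents: questionnaires at 3 months, 1 year and 2 years, taken as days 91, 365 and 730. Assumed, because the documents give nothing: lognormal return times with median *m* and log-SD *s*, rounded up to whole days (which adds about 0.5 day to a mean), and a fraction *f* who never return.

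**Step 1: non-return unrelated to the returners' times.**

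- Share returned by day 730 = (1 − f) × Φ(ln(730/m)/s).
- Mean among returners = m·exp(s²/2) × Φ(ln(730/m)/s − s) ÷ Φ(ln(730/m)/s). The factor (1 − f) cancels, so *f* drops out.

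For m = 120 and s = 0.7: ln(730/120)/0.7 = 2.579, Φ = 0.9951, and m·exp(s²/2) = 153.3. The returners' mean is 153.3 × Φ(1.879) ÷ 0.9951 = 153.3 × 0.9699 ÷ 0.9951 = 149.4, or 150 days after rounding up.

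| Never return | Mean, 120/0.7 | Returned by 2 years | Mean, 42/0.7 | Returned by 2 years |
|---|---|---|---|---|
| 0% | 150 days | 99.5% | 54 days | 100% |
| 5% | 150 days | 94.5% | 54 days | 95% |
| 10% | 150 days | 89.6% | 54 days | 90% |
| 20% | 150 days | 79.6% | 54 days | 80% |

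For 120/0.7 the median over all subjects, which does respond, is 120, 126, 133 and 150 days.

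**Step 2: slow recovery and non-return linked.** Take m = 180 and s = 1.0 with no separate never-returners, so non-return is simply the slow tail. ln(730/180) = 1.400 and Φ = 0.919, so 8.1% have not returned at 2 years. The true mean is 180 × exp(0.5) = 297 days. The returners' mean is 297 × Φ(0.400) ÷ 0.919 = 297 × 0.6555 ÷ 0.919, or about 212 days. Here the mean has moved, but it is still well below 297, and nothing shows the 8.1%.

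**Step 3: an early summary.** For 120/0.7 cut at day 91: ln(91/120)/0.7 = −0.395, so 34.6% have returned. Their mean is 153.3 × Φ(−1.095) ÷ 0.346 = 153.3 × 0.1367 ÷ 0.346, or about 61 days after rounding up, against 153 overall.

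**Step 4: loss alone.** With 20% loss spread evenly over the three intervals and everyone eventually returning, the returners' mean falls by only 0.8 days (42/0.7) to 7.1 days (180/1.0). Loss by itself is a small part of the problem.

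**Step 5: what a percentage needs.** Take 120/0.7, 10% never returning, 20% lost overall, and 80% of never-returners lost. The loss among the other 90% is (0.20 − 0.10 × 0.80)/0.90 = 13.3%.

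- Returned among 2-year completers: 0.90 × 0.867 × 0.995 ÷ 0.80 = 97.0%.
- Returns reported before loss: 0.90 × 0.133/3 × (0.346 + 0.944) = 5.2% of all enrolled.
- Returned over all enrolled: 77.6% + 5.2% = 82.8%.
- Returned over those with any questionnaire: 82.8 ÷ 93.3 = 88.7%.
- Truth: 89.6%. Kaplan-Meier in a simulation of the same case: 96.0%.

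So the denominator must be stated. The completer percentage is more optimistic than Kaplan-Meier, and both are too high here.

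**The case against.** The strongest reply is that little depends on this. These are two of four parameters within one of six secondary outcomes, with no test, comparator or threshold. ASES and Constant scores, additional surgery, satisfaction and serious adverse events (which include "Results in persistent or significant disability/incapacity") would partly reveal poor recovery. Non-return could be close to zero. All of that stands and limits the severity. It does not close the gap, because none of those measures reports return itself, and for a descriptive outcome the summary is the whole result.

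The contrast with sections 4.4.1 and 4.4.2 should not be pressed hard either: adverse events and technical success are binary, so a rate or proportion is their natural form. An n printed beside the mean would also expose part of the problem, but the plan does not call for one here.

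A reader might infer three stronger things that the documents do not support:

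- *That the mean can never respond to non-return.* This holds only when non-return is unrelated to the returners' times. Step 2 shows the mean moving when the two are linked.
- *That non-return is not collected.* The questionnaire and case report forms are not in the documents and may well record it. The gap shown is in the planned summary.
- *That the plan expects 60% attrition,* because 150 enrolled are to allow 30 + 30 = 60 evaluable. Both numbers are ceilings, and the margin may also cover uneven recruitment between criteria 2A and 2B. It is not a forecast of loss.

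**Conclusion.** The point holds as a minor one. The only statistic named for these two outcomes is defined for returners alone, and no section supplies a count, a percentage, an assigned value or a censoring rule for the others. That follows from the text and needs no distributional assumption.

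The size is unknown. The day counts and percentages rest on assumed lognormal times, assumed never-return fractions and assumed loss. The constancy of the mean in step 1 rests further on non-return being unrelated to the returners' times. Where the two are linked, the mean moves but stays too low. The understatement is largest in early or interim summaries.

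No hypothesis test, sample size or study decision is affected. This is a cheap improvement to reporting and does not threaten the study's main conclusion.

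**What to change.** In section 4.4.5, for these two outcomes only:

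1. At 3 months, 1 year and 2 years, report the number returned, the number known not to have returned and the number with unknown status. Give the percentage returned over all enrolled subjects (all enrolled employed subjects for work) and also over those assessed at that visit.
2. Report the Kaplan-Meier median time to return with a 95% confidence interval, censoring subjects without a reported return at their last completed questionnaire.
3. If mean ± SD is kept, label it as among subjects who returned and give n.
4. State that the percentage among assessed subjects and the Kaplan-Meier estimate both look too favourable if non-returners are lost more often.

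Sling days and the number of therapy visits can stay as mean ± SD.

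The cost is a few sentences and standard code at the existing visits. If the questionnaire already records that a subject has not yet returned, no new data are needed; otherwise one item must be added. The downsides are slightly more analysis, a less favourable summary, and limited precision. At the planned numbers, 27 of 30 returned is 90% with an exact 95% interval of 73.5% to 97.9%, and return to work will be less precise because only employed subjects count.
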